11.0 PREMATURE DISCONTINUATION FROM STUDY DRUG

The Investigator will continue to monitor subjects who have discontinued prematurely from study drug due to an AE (serious and nonserious) until resolution or stabilization of the AE.

The Investigator must complete all applicable CRF pages for subjects who discontinue study drug prematurely. Final visit procedures (i.e., AE assessment, concomitant medications review, targeted physical exam, vital signs, and weight) should be conducted for any subject who discontinues study drug prematurely.

Subjects who prematurely discontinue study drug for any reason other than toxicity may be re-entered into the study after consultation between the Investigator and the Sponsor or the Sponsor's designee. Dosing of a subject who previously discontinued in the study is at the discretion of the Sponsor. However, subjects who drop out due to toxicity will not be replaced.

12.0 PRODUCT SPECIFICATIONS

12.1 Description

Gablofen® (baclofen injection) is provided in a single use pre-filled syringe of 60,000 mcg per 20 mL (3000 mcg/mL) for intrathecal administration only.

The drug product is manufactured under current Good Manufacturing Practices (cGMP) at Cangene BioPharma, a contract manufacturing facility that has undergone FDA inspection.

12.2 Formulation, Packaging, and Labeling

Gablofen® (baclofen injection) 3 mg/mL will be supplied in single use pre-filled syringes and contains baclofen, sodium chloride and water. Syringes will be packaged in boxes for shipment to the clinical sites.

Study drug syringes will be affixed with a single label panel containing the following information:

Gablofen® (baclofen injection) Intrathecal
60,000 mcg / 20 mL (3,000 mcg/mL)
Lot Number: XXXXXX
Manufacturing Date: MM-DD-YYYY
Store at Room Temperature (15-30°C)
Caution: New Drug – Limited by U.S. Federal Law to Investigational Use
Distributed by Mallinckrodt Brands Pharmaceutical, Inc.

12.3 Receipt, Storage and Stability of Gablofen

Gablofen® (baclofen injection) 3 mg/mL syringes will be packaged in boxes for shipment to investigational sites. Excursions permitted to 4 - 30°C (6° to 86 °F), and after receipt should be stored at 15 - 30 °C (59 °- 86°F) until use.

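### The lower limit for permitted temperature excursions in Protocol 12.3 is given as 4 °C and as 6 °F, and these differ by 33.2 °F (18.4 °C)

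*Protocol*

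**What the plan says.** Protocol 12.3 describes how the 3 mg/mL syringes are shipped and stored. It gives two temperature ranges, each in Celsius with a Fahrenheit equivalent in brackets:

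- Permitted excursions: "Excursions permitted to 4 - 30°C (6° to 86 °F").
- Storage at the site: "after receipt should be stored at 15 - 30 °C (59 °- 86°F) until use".

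For context, the syringe label in Protocol 12.2 carries the storage range in Celsius only: "Store at Room Temperature (15-30°C"). It agrees with the storage range in 12.3 and gives no excursion limit. Section 12.2 also says that the product "contains baclofen, sodium chloride and water", so it is a water-based solution. Section 12.1 says that it is for intrathecal use only.

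Nothing else in the supplied protocol or SAP gives an excursion range or warns against freezing, so no other text settles which lower limit is meant.

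**The concern.** A range printed in two units should give the same answer in both. Here the lower excursion limit is a few degrees above the freezing point of water in Celsius and far below it in Fahrenheit. Someone judging a cold excursion would permit it or not depending on which unit they read.

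This is a product-handling instruction, not background text. The sites work under US rules (the label in 12.2 carries the US federal investigational-use caution), so use of the Fahrenheit figure is realistic. Under Protocol 12.4 the only preparation is filling the pump, and the accountability items in 12.6 do not include temperature. The supplied text therefore shows no later step designed to catch a decision made on the wrong figure.

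What is at stake is how an intrathecal product is handled. The point does not touch the endpoint, the sample size or any analysis.

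**Working it through.** **Inputs, all from Protocol 12.3**

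| Limit | Celsius | Fahrenheit |
|---|---|---|
| Excursion, lower | 4 | 6 |
| Excursion, upper | 30 | 86 |
| Storage, lower | 15 | 59 |
| Storage, upper | 30 | 86 |

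**Formulas:** F = C × 9/5 + 32 and C = (F − 32) × 5/9.

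**Step 1. Reproduce the figures that should agree.**
- 30 × 9/5 + 32 = 86.0 °F. This matches both upper limits.
- 15 × 9/5 + 32 = 59.0 °F. This matches the lower storage limit.

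Three of the four pairs convert exactly.

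**Step 2. Convert the lower excursion limit in both directions.**
- 4 × 9/5 + 32 = 39.2 °F, where the text gives 6 °F.
- (6 − 32) × 5/9 = −14.4 °C, where the text gives 4 °C.

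**Step 3. Size of the gap.**
- In Fahrenheit: 39.2 − 6 = 33.2 °F.
- In Celsius: 4 − (−14.4) = 18.4 °C.

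Rounding cannot explain this. 39.2 °F rounded to a whole degree is 39 °F, which is 3.9 °C.

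**Step 4. Position relative to freezing.** Water freezes at 32 °F, and 32 − 6 = 26, so the Fahrenheit limit lies 26 °F below that point. Of the 33.2 °F over which the two units disagree, 26 °F (26/33.2 = 78%) is below the freezing point of water. For example, a reading of 20 °F is (20 − 32) × 5/9 = −6.7 °C: it is inside the Fahrenheit range and outside the Celsius range.

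**Step 5. Could a simple slip account for the figure?**
- If 6 was meant in Celsius, it would be 6 × 9/5 + 32 = 42.8 °F, which does not match 4 °C.
- If a leading digit was lost, the values nearest 39.2 are 36 °F (2.2 °C) and 46 °F (7.8 °C). Neither is 4 °C. Either would cut the gap to 39.2 − 36 = 3.2 °F or 46 − 39.2 = 6.8 °F, and both lie above freezing.

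None of these readings makes the pair agree, and the arithmetic cannot say which of the two printed limits was intended.

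**The case against.** The arithmetic is not in dispute. The case on the other side concerns where the figure came from and what follows from it.

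**The figure may be a reading error.** The text was read from PDF by a program. The spacing around the degree signs in this sentence is irregular, and Appendix A in the same text misspells the product name several times. A damaged character cannot be excluded. This stands, and it is why the fix begins with the source file. If a leading digit was lost, the mismatch would be smaller and the freezing question could disappear (Step 5).

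**No acceptance procedure is described.** Sections 12.2 to 12.6 mention no temperature logger, no temperature check on receipt and no rule for accepting or rejecting a shipment. A reader might infer that sites apply the figure as a formal acceptance limit. The text says only that excursions within the range are permitted. This stands.

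**The chain to harm is not documented.** A reader might infer that frozen syringes would be infused. That would need a sub-freezing excursion, a record read in Fahrenheit, a site that passes over the Celsius figure printed first, no query about an obviously mismatched pair, and use of the syringe. The documents support none of these as fact. They give neither the product's freezing point nor the effect of freezing. The dissolved salt would lower the freezing point below that of water by an amount that cannot be worked out, because its concentration is not stated. This stands: the most that can be said is that a site could treat such an excursion as permitted.

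**Confounding is not supported.** Because the study has no control group, a reader might infer that a handling effect could be mistaken for an effect of the 3 mg/mL concentration. The primary endpoint (Protocol 3.2.1 and 3.3) requires an intradural mass on infusion MRI. Nothing in the documents links freezing to that finding or to any other adverse event, so this inference should not be drawn.

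**Routine storage is unaffected.** The range after receipt converts correctly and agrees with the label. The mismatch bears only on excursions, which the order of the text in 12.3 suggests are mainly those in shipment.

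What remains is that, as the text reads, an operating limit contradicts itself and nothing else in the documents resolves it.

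**Conclusion.** The point holds as an internal contradiction in one product-handling figure. The lower excursion limit is stated as 4 °C and as 6 °F, which are 33.2 °F (18.4 °C) apart. Between 6 °F and 39.2 °F an excursion is permitted in one unit and not in the other, and most of that interval is below the freezing point of water.

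The consequence is limited. A site relying on the Fahrenheit figure could treat a sub-freezing excursion as permitted. The documents do not show that any shipment was exposed, that any decision was made on the Fahrenheit figure, or that the product would be altered.

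The conclusion assumes that the extracted text reproduces the protocol correctly at this character. It makes no assumption about which lower limit is right; the documents do not say, and only the sponsor's stability data can.

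**What to change.** 1. Check the lower excursion limit in the source file of the protocol, to rule out an extraction error.
2. If the mismatch is there, reconcile the two lower limits against the sponsor's stability data.
3. State one lower excursion limit in Protocol 12.3, correctly converted in both units.
4. Tell sites of the correction.

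The cost is one look-up in the source file, one check of the stability data (assumed to be in the sponsor's hands), one corrected figure and a short notice to sites. No analysis, table or sample-size statement changes. The documents give no evidence of an affected shipment, so this point does not call for a retrospective review of shipments.

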12.4 Preparation and Administration of Study Drug

There is no manipulation or preparation of study drug other than filling into the SynchroMed® II Infusion Pump according to the manufacturer's instructions.

12.5 Ordering and Distribution of Study Drug

Study drug may be requested by submission of a medication request form. The form may be submitted to the Sponsor or designee by facsimile or electronic mail PDF as per the instructions on the drug ordering form.

12.6 Accountability of Study Drugs

All study drug received, dispensed, and returned must be accounted for in the study drug Dispensing Log, including:

- Subject number and initials
- Date study drug was dispensed
- Quantity dispensed
- Quantity returned
- Amount wasted including drug removed from a pump during refills or pump replacement

All study drug received and dispensed by the Investigator will be inventoried and accounted for throughout the study. The study drug must be stored in a restricted area with limited access. Contents of the study drug containers must not be combined.

The Investigator must maintain an accurate, up to date Dispensing Log for all study drugs supplied by the Sponsor. Study drug dispensed for all subjects must be recorded on the Drug Accountability Form. The study drug Dispensing Log and remaining drug inventory will be reviewed during monitoring visits by the Sponsor-designated clinical monitor.

The study drug supplied for this study is for use only in subjects properly consented and enrolled into this protocol. Study drugs must be kept in a secure location physically separated from standard clinic or office drug supplies.

13.0 SAFETY MONITORING AND ADVERSE EVENTS

13.1 Adverse Events

Data regarding treatment-emergent AEs will be collected in this study. Treatment-emergent AEs are events that are not present at baseline, or if present at baseline, have worsened in severity.

The descriptions and grading scales found in the CTCAE v 4.03 will be used for AE reporting. A copy of the CTCAE v 4.03 is provided in [Appendix B](#).

The medical monitor and contact information for this study are presented below:

[name]	Director, Clinical Affairs, Mallinckrodt, Inc.	Office: [contact] [contact]	E-mail: [contact]
---------------	--	--	---

Evaluation of Adverse Events and Adverse Drug Reactions:

Adverse events in the Case Report Form (CRF) will be classified according to the most recent FDA definitions and in a manner consistent with ICH guidelines. As such the following definitions will be used:

An adverse event (AE) is any unfavorable and unintended sign, symptom, or disease temporally associated with the use of an investigational (medicinal) product (IP) or other protocol-imposed intervention, regardless of attribution. An AE may include intercurrent illnesses or injuries that represent an exacerbation (increase in frequency, severity, or specificity) of pre-existing conditions (e.g., worsening of asthma). A laboratory abnormality will be reported on the “Adverse Event” case report form only if it is associated with clinical sequelae or requires therapeutic intervention. Whenever possible, it is preferable to record a diagnosis as the AE term rather than a series of symptoms relating to a diagnosis. AEs will be graded according to the NCI [Common Terminology Criteria for Adverse Events \(CTCAE\) v 4.03](#).

The reporting period for nonserious AEs starts after the first administration of study drug on Day 1 and ends after discontinuation of study medication.

If a SAE remains unresolved after discontinuation of study medication, the subject will be followed, at the investigator’s discretion, until resolution of the event. SAEs must be followed until resolution by the PI, even if this extends beyond the study-reporting period. Resolution is defined as the return to baseline status or stabilization of the condition with the expectation that it will remain chronic.

The investigator will assess AEs for severity, for relationship to IP, and as to whether the event meets one or more of the definitions of an SAE.

The investigator will determine the relationship of an AE to the IP and will record it on the source documents and AE CRF, using the categories of unrelated, possibly related (ie, reasonable possibility of causal relationship associated with use of IP), and probably related (ie, probably or known reason to conclude that use of IP caused the event).

In order to classify adverse events and diseases, preferred terms will be assigned by the sponsor or its designee to the original terms entered on the CRF, using MedDRA. CTCAE is provided in [Appendix B](#).

Table 13-1: Severity Assessment Terminology for Reporting Adverse Events (CTCAE v 4.03)

CTCAE Grade	Common Term	Description
1	Mild	Mild; asymptomatic or mild symptoms; clinical or diagnostic observations only; intervention not indicated.
2	Moderate	Moderate; minimal, local or noninvasive intervention indicated; limiting age-appropriate instrumental Activities of Daily Living (ADL).
3	Severe	Severe or medically significant but not immediately life-threatening; hospitalization or prolongation of hospitalization indicated; disabling; limiting self-care Activities of Daily Living (ADL).
4	Life-Threatening	Life-threatening consequences; urgent intervention indicated.
5	Death	Outcome of AE was death

For those AEs that are not described on the CTCAE v 4.03, such AEs will be graded according to the same scale as defined above.

13.2 Serious Adverse Events

According to the ICH Guidelines for Good Clinical Practice (E6), an SAE is any untoward medical occurrence during the course of a clinical investigation that is characterized by one or more of the following:

- Results in death
- Is life-threatening
- Requires nonscheduled (not routine or planned) in-subject hospitalization or prolongation of existing hospitalization
- Results in persistent or significant disability/incapacity
- Is a congenital anomaly/birth defect
- Important medical events

Although not a formal SAE, exposure to study drug during pregnancy, even if no AE is reported in the mother, should be reported within 24 hours as an SAE.

For subjects who are hospitalized for a scheduled procedure or observation related to failures of the pump, catheter or other device malfunctions, and where the event is not related to the study medication, the hospitalization will not be considered an SAE as part of this clinical trial unless deemed possibly related to study medication by the investigator or Medical Monitor. Please contact the Medical Monitor prior to any scheduled hospitalization, for catheter or pump related corrections, to determine if this event should be recorded as an SAE or will be considered routine standard of care.

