13.2.1 Reporting Requirements for Serious Adverse Events

Initial Reporting

SAEs (based on FDA/ICH definition of an SAE) require immediate reporting to Mallinckrodt or designated representative.

For all fatal or life-threatening events, the investigator(s) or designee must report information within 24 hours to the Medical Monitor at [contact].

For all SAEs, the investigator(s) or designee must complete the SAE report form with the minimum information required by FDA and ICH and fax it to Mallinckrodt Pharmacovigilance at [contact] within 24 hours of first knowledge of the event even if the experience does not appear to be related to the study drug.

The investigator(s) or designee will receive acknowledgement of receipt of the SAE report form from Mallinckrodt.

Should the investigator(s) or designee have any difficulty in sending the SAE report, they may contact Mallinckrodt Pharmacovigilance at [name] (24 hour call center) or email: [contact].

If there is any doubt about whether the information constitutes an SAE, the information is to be treated as an SAE.

Follow Up Reporting

The investigator(s) or designee must complete an SAE report form for all follow-up information received and fax it to the sponsor [contact] within 24 hours of receipt of additional or updated information (eg, detailed written descriptions that include copies of relevant subject records, autopsy reports and other supporting documents). The investigator(s) or designee will receive acknowledgement of receipt for each SAE report form from Mallinckrodt.

The investigator(s) or designee is required to report immediately unexpected SAEs to the responsible IRB/IEC.

All adverse events (serious and non-serious) occurring in subjects from the time of informed consent through the completion of the follow-up telephone call will be documented as an AE in the source and in the eCRF. All fields on the AE eCRF page should be completed for each event with a full description of the event and date and time of onset and resolution. The investigator must follow up on all AEs and SAEs until the events have subsided, until values return to within the acceptable range, the investigator determines that follow-up is no longer necessary, or the subject is referred to a nonstudy physician.

The sponsor will report SAEs to the FDA and investigators according to local regulations.

Table 13–2 Reporting Requirements for Adverse Events

Reporting Requirements for Adverse Events		

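### Scheduled admissions for pump or catheter failure count as SAEs only if judged possibly drug-related, so the SAE summary can omit on-study catheter admissions

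*Protocol*

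**What the plan says.** Protocol 13.2 defines an SAE by outcome. The hospitalisation criterion is "Requires nonscheduled (not routine or planned) in-subject hospitalization or prolongation of existing hospitalization", with no causality test.

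The same section then adds a special rule. It opens "For subjects who are hospitalized for a scheduled procedure or observation related to failures of the pump, catheter or other device malfunctions", is limited to events not related to study medication, and concludes that "the hospitalization will not be considered an SAE as part of this clinical trial unless deemed possibly related to study medication" by the investigator or the Medical Monitor. Sites are to contact the Medical Monitor before any scheduled admission for a catheter or pump correction "to determine if this event should be recorded as an SAE or will be considered routine standard of care".

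Two other sections bear on this:

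- Protocol 13.1 has the investigator assess severity, relationship to the product, and, as a further item, "as to whether the event meets one or more of the definitions of an SAE".
- Protocol 13.2.1 requires every SAE to be reported "within 24 hours of first knowledge of the event even if the experience does not appear to be related to the study drug", and adds: "If there is any doubt about whether the information constitutes an SAE, the information is to be treated as an SAE".

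SAP 10.4 plans a summary and listing of deaths and other SAEs. SAP 10.3 promises full detail on any SAE report relating to a granuloma.

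**The concern.** Seriousness and causality are normally two separate judgements, so that a serious-event table shows what happened to subjects before anyone attributes a cause. Here, for one class of admission, the causality judgement decides whether the event enters the table at all.

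The class matters because catheter-tip complications are the study's main safety question, and the protocol itself says that granuloma and catheter failure can look alike. The study is single-arm and open-label, and is meant to support a marketing application (Protocol 1.4, 3.4.1). Its descriptive safety tables are its main product. A causality filter on the serious-event count is a weakness that a regulatory reader could fairly question.

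**Working it through.** The plan gives no figure for device admissions or expected SAEs, so there is nothing to reproduce. The check sets the rules side by side and then bounds the size under a stated assumption.

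**1. Which admissions are affected.** The special rule covers scheduled admissions only. An unplanned admission for catheter failure still meets the listed hospitalisation criterion, whatever its cause.

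**2. How wide 'scheduled' is.** Neither the listed criterion nor the special rule says scheduled relative to what. Nothing limits the word to admissions planned before enrolment or first dose. A revision booked some days after an on-study failure is scheduled in the ordinary sense. It is also unclear whether 'scheduled' governs 'observation' as well as 'procedure'. The special rule names failures and malfunctions, so it is clearly meant to reach events that arise on study.

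**3. What decides SAE status.** Within the class, the only stated route back to SAE status is a judgement of possible relatedness. Protocol 13.1 lists relationship and seriousness as separate assessments. Protocol 13.2.1 makes apparent unrelatedness no reason to withhold a report and resolves doubt towards an SAE. Protocol 13.2 instead sends the question to a case-by-case discussion, without written criteria and without requiring that granuloma be excluded first. That discussion takes place before the admission, so possibly before the cause of the failure is known.

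**4. Why a granuloma could be involved.**
- Protocol 3.3 treats a sudden loss of response as a granuloma sign only when it is not put down to a mechanical or catheter cause.
- Protocol 1.4 says granuloma-like symptoms may turn out to come from a blocked catheter.
- Protocol 1.1 describes three possible cases, from a cited review, that rested on reduced catheter flow and were resolved by moving or changing the catheter.
- Protocol 3.3.1 lists catheter withdrawal and replacement among the interventions for granuloma, the same kind of procedure as a catheter repair.

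An early attribution to catheter failure can therefore remove loss of response as a granuloma sign and, if the admission is scheduled, its SAE status too.

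**5. What the other outputs show.** SAP 10.8.2 summarises catheter-related events with a 95% confidence interval. SAP 7.3 covers pump and catheter replacement by age group. SAP 10.2 summarises AEs by severity. None of them identifies which events led to admission.

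**6. Size.** The only documented input is the maximum enrolment of 150 (Protocol 14.1, SAP 5.1). Assume that 5% to 15% of subjects have a device admission within 12 months:

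- 150 × 0.05 = 7.5, about 8 subjects
- 150 × 0.15 = 22.5, about 23 subjects

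This is a ceiling, because it treats every admission as scheduled and judged unrelated. If only 25% to 75% meet both conditions (a second assumption):

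- 7.5 × 0.25 = 1.9, about 2 subjects
- 22.5 × 0.75 = 16.9, about 17 subjects

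**The case against.** The strongest reply is that the rule is narrow and that the study's main result does not depend on it.

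- **Scope.** A reader might infer that all hospitalisation for pump or catheter failure leaves the SAE table unless drug-related. The text does not support that. Nonscheduled admissions stay SAEs, and important medical events are a separate listed criterion. This stands and limits the point.
- **Recovery.** Either the investigator or the Medical Monitor can judge the event possibly related, with no time limit, and the doubt rule favours SAE status. This also stands: omission is possible, not certain. But the doubt rule and the special rule pull in different directions, and the protocol does not say which prevails.
- **Primary endpoint.** A reader might infer that the granuloma rate itself is biased downward. It is not derived from SAE status. It rests on clinical signs plus MRI (Protocol 3.2.1, 3.3), with MRIs read by a central radiologist blinded to history, and every granuloma is listed (SAP 10.3).
- **Capture elsewhere.** All AEs go on the CRF. The Medical Monitor is told of catheter surgery and pump replacement (Protocol 3.5.5). SAP 7.3 and 10.8.2 summarise replacements and catheter events. CTCAE grade 3 refers to hospitalisation, so severity is a partial marker. The underlying events are not lost. What is missing is the link from event to admission.
- **Dilution.** Counting every on-study device admission as an SAE would bring in battery replacements, which Protocol 3.5.5 anticipates. That is a fair objection to a single undivided SAE count, and the fix should allow for it.

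That the judgement is unblinded adds little, since relatedness is always judged unblinded in a single-arm study.

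**Conclusion.** The point holds for scheduled admissions. For these, Protocol 13.2 makes seriousness depend on causality, contrary to 13.1 and 13.2.1. Because 'scheduled' is undefined, an admission arising from an on-study catheter failure can drop out of the SAE summary. That could include an admission where a granuloma is first taken for catheter failure. The effect is on SAE reporting and on descriptive SAE tables; no SAE rate is tested (SAP 2.2, 10).

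The number affected cannot be derived. A reader might take 8-23 as the expected number of missing subjects. It is only an upper bound, and it rests on an assumed admission rate of 5-15% in 150 subjects. The problem is worth correcting before the safety tables are produced, because the remedy is specific and cheap.

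**What to change.** 1. **Protocol 13.2:** reconcile it with 13.1 and 13.2.1 so that seriousness is assessed independently of relatedness. Define 'scheduled' as planned before the first dose, and use the same meaning in the listed hospitalisation criterion.
2. **CRF:** record every other pump, catheter or device admission with its seriousness, its relationship to study drug and its granuloma classification. Do this even if the sponsor keeps an exemption from expedited reporting for some of them.
3. **SAP 10.4:** show SAEs with and without device-related admissions, so that routine replacements such as battery changes can be seen separately and do not obscure the remaining SAEs.

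The cost is a protocol wording change, some added CRF entries and an extra table row. The SAE count will be higher when device admissions are included. The two-way display lets a reader see how much of the rise comes from them.
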